To explore the possibility that the effect of the intervention depends on certain other variables (i.e. moderation or effect modification), we will examine whether potential moderators statistically interact with the intervention condition, resulting in differential intervention effects. This is accomplished by adding a third term to the group by time interaction, creating a three-way interaction term. The multilevel model can accommodate moderators at the individual or cluster level (e.g. a cross-level interaction). Consistent with the FOA we are responding to, a moderator of particular interest is Latin American country of origin. Given the composition of the day labor pool in Houston, with a predominant Mexican population, we will examine country of origin as Mexico v. Central America. These methods are applicable for other potential moderators, like individual characteristics (e.g. demographic variables, anxiety, alcohol use) and characteristics of the street corners (e.g. size).

AIM 2 Determine the mediating effect of psychosocial stressors on VALES+Tú primary outcomes. To determine whether situational and immigration stress mediate the relation between the intervention and outcome (i.e. whether these variables "carry" the intervention effect), we will use cross-level

mediation analysis, which accommodates a situation where the intervention is assigned at the cluster level, but the proposed mediator and the outcome are measured repeatedly over time. A conceptual model of the proposed analysis is shown in the figure below. We will use a version of the widely accepted product of coefficients methods with bias corrected bootstrapped confidence intervals, adapted for longitudinal designs with a randomized intervention assigned at the cluster level. The product of coefficients method has been shown to have greater statistical power than the Baron and Kenny causal steps method. In the three-level operationalization of mediation analysis, two models are specified: 1) A three-level model (street corners, individuals, and repeated measurements) with the mediator as the dependent variable and intervention condition, time and the intervention by time interaction (path a) as the predictors; and 2) a separate three-level model with the outcome (e.g. workplace hazards) as the dependent variable, and intervention condition, time, the mediator (treated as a time-varying covariate; path b), and the intervention by time interaction as predictors. The product of paths a (intervention effect to mediator) and b (mediator to outcome) from model 1 and model 2, respectively, is the mediated effect. Bootstrap resampling methods are then used to compute bias-corrected 95% confidence intervals for purposes of significance testing.

Ethics

IRB approval will be sought from CPHS. State whether IRB approval will be sought from CPHS or another IRB (under UT System Reciprocity Agreement).

Study personnel will explain the nature of the study and the benefits and risks of participating. LDL will be assured that they can pause the interview if they are offered a job and resume the interview later. Consent will be sought after this process, and eligible LDL wishing to participate will signify their consent by selecting the appropriate button presented on the iPad used to present the consent form.

Data handling and record keeping

Access to source documents will be limited to the Principal Investigator and other Key Personnel. Electronic records will be stored on password protected personal computers and on the University server. Records will be retained in accordance with applicable regulations. Paper records will be stored in locked cabinets.

Participants will be assigned a unique study number. This number will be used to track data and other records. It will be necessary to collect names and contact information (including that for selected

friends and family) so that participants can be reached to schedule their follow-up interviews. This information will be stored in separated files and will be accessed on a need to know basis.

Surveys will be conducted using iPads. When not in use, iPads will be stored in locked cabinets. Completed surveys will be downloaded on a regular basis by the data manager.

Quality control and assurance

All data collection procedures and instruments will be pilot tested and revised as necessary. Computerized surveys will be programed to minimize out of range, inconsistent, or missing date.

The data manager will regularly audit data for problematic entries and provide feedback to the Principal Investigator and data collectors.

We do not have plans to employ third party monitoring.

Publication Plan

Manuscripts will be prepared for submission to relevant peer reviewed journals. Anticipated manuscripts will address participants' characteristics at baseline and the significance of changes in workplace injury and psychosocial items from baseline to follow-up within and between intervention groups.

We do not anticipate retuning results to participants.

ATTACHMENTS

- 1. Schematic of Study Design
- 2. Study Schedule
- 3. Consent Document
- 4. Case Report Form

COVID-19 Supplemental Study

Background and Rationale

The Vales+ Tu injury prevention study was awarded a supplemental grant from the National Institute on Minority health and Health Disparities (3R01MD012928-03S1). The purpose of the supplemental study is to assess the impact of the COVID-19 pandemic on Latino Day Laborers and their ability to adhere and implement COVID-19 mitigation practices.

LDL are routinely exposed to multiple interrelated stressors associated with both their work and their immigration status such as temporary work, crowded living conditions, and food insecurity. While the stressors are not new, they have been intensified by the COVID-19 pandemic as evidenced by their Latino's high COVID-19 mortality and morbidity rate.

Objectives

The study will address this question: How do stressors and protective factors experienced in the context of the COVID-19 pandemic influence the mental health of Latino day laborers and impact their ability to adhere to COVID-19 mitigation practices? To answer this question, our research will be guided by the following aims:

- 1. Describe Latino day laborers' adherence to COVID-19 mitigation practices and identify the barriers and facilitators associated with their adoption.
 - a. Conduct two focus groups stratified by age and corner (i.e. public hiring location) with 16 LDL to characterize barriers and facilitators associated with COVID 19 mitigation practices.
 - Administer a survey to 300 Latino day laborers.
- 2. Using a Structural Modeling approach, determine the impact of social, psychological and economic stressors on LDL mental health and their compliance with COVID-19 mitigation practices.
 - a. The Measurement Model: Use Aim 1 survey data to conduct a confirmatory factor analysis to develop good-fitting measures of stressors, protective factors, mental health and adherence to COVID-19 mitigation practices.
 - b. The Structural Model: Use structural equation modeling to test hypothesized relationships among and between the latent variables to identify mediators and moderators that will point to plausible intervention strategies to increase compliance with COVID-19 mitigation practices.

Survey Approach

Study Population and sampling. We plan to recruit approximately 300 LDL, a size comparable to our samples in previous studies. We will recruit participants in the field at locations ("corners") where LDL congregate to seek employment. We will recruit from corners identified from our previous studies.

Corner selection. Field team will visit randomly selected corners identified in our parent study. We will follow the same corner selection procedure specified in the parent study to recruit participants. Our total sample size will be 300 participants.

Participant eligibility: Eligible participants will be 18 years of age or older, self-identify as Latino, be at the corner looking for work, and have a previous history of seeking employment at the corner or similar locations. LDL will also be asked if they have experienced symptoms of COVID-19 in the previous 48 hours (fever, cough, sore throat, fatigue, etc.). Those reporting symptoms will be thanked for their time and informed they are not eligible to participate and will be given a brochure with COVID related resources.

Obtaining Informed Consent: Participants will be asked to provide oral informed consent to take part in the survey. Potential participants will be told the purpose of the assessment, that they can refuse to

answer any item and that they can pause the assessment to talk to potential employers or attend a job. The interviewer will explain that the study has been granted a Certificate of Confidentiality and that all responses will be protected. If the potential study participant does not provide informed consent, he will be thanked for his time but will not be able to take part in the survey.

Survey interview. The interviewers will visit the selected corners and approach LDL about participating in our study. After explaining the purpose of the study and verifying requirements, the interviewer will obtain oral informed consent and administer the Assessment. Responses will be recorded using Qualtrics installed on iPad tablets. The COVID-19 survey will be conducted at least eight weeks after completion of the parent study post-test survey, which is conducted one to two months after the baseline survey.

Given the ongoing COVID-19 pandemic, the field team will continue to adhere to COVID-19 mitigation practices such as mask use and social distancing when interacting with LDL in the field. All field staff are familiar with these practices as they were implemented and tested during implementation of the parent study. Field team members have been trained in, and have experience with, approaching and recruiting potential participants, determining eligibility, obtaining informed consent, and administering surveys. However, they will receive additional training and get familiar with administering the current survey before recruitment starts.

Compensation: Participants who complete the COVID-19 survey will receive a one time incentive payment of \$100 in the form of a Visa gift card. We are providing a higher than usual incentive payment due to the fact that the interview will be long (60-75 minutes), and it may prevent some participants from getting hired for the day. Even when they will be encouraged to attend to their job search activities and return to the interview the following day, many day laborers may choose to attend to the interview with the unclear expectation that they will get a job later in the day. The incentive will partly cover the possible loss of partial or full employment for that day. Gift card distribution will be tracked and properly documented.

Survey measures. The survey to be administered to study participants will include an array of measures to answer our proposed aims. Some of the measure include, but are not limited to, COVID-19 Psychosocial factors, COVID-19 mitigation practices, Socio-Economic Stressors, Mental Health Measures, Protective Factors, and COVID-19 vaccination beliefs. Please refer to the COVID-19 survey table of contents for a list of all measures to be collected.

Data Analysis.

The primary goal of AIM 1 is to provide a careful description of the LDL who seek work at the corners during this pandemic. Survey items are based on the priorities identified in Aim 1 and on a more recent literature review of measures of practices and behavioral determinants which reflect the most recent changes in the pandemic.

Initially, we will look for evidence of variability and patterns of missing data, and check for data accuracy and adherence to the assumptions of planned statistical procedures. The primary statistical analyses to

be conducted to satisfy AIM 1 will be descriptive (means, frequencies, correlations) in order to understand how participants vary by time in the US, age, corner type, and other critical factors. We will look at frequency distributions or calculate means and standard deviations for responses to all questions on the questionnaire, and evaluate differences in proportions or means by salient sample characteristics using appropriate statistics. A significance level of 0.05 will be used to identify critical subgroup differences. However, since we are conducting these analyses primarily for description, and we are conducting multiple tests, we realize the limitations of any test of significance and will interpret results accordingly. The descriptive analyses conducted to satisfy AIM 1 will provide a good profile of LDL working during this pandemic and will be used to insure that data meet the requirements for answering the more complex questions of AIM 2.

The goal of Aim 2 is to use a Structural Equation Modeling approach to determine the impact of social, psychological and economic stressors on LDL mental health and their compliance with COVID 19 mitigation practices. We understand the determinants of COVID 19 mitigation practices as a set of conditions, behaviors, cognitions and exposures that lead to health inequalities as proposed by Adler and Ostrove's Pathways to Health framework. This model posits that structural conditions in the lives of individuals facilitate or constrain their access to environmental resources, shape their psychological makeup and influence exposure to pathogens, stress responses and performance of health behaviors. While this model describes distal and proximal influences on health, we are adapting it to address the COVID 19 pandemic as a current event that has multiple and simultaneous influences on the structural, social and psychological stressors experienced by Latino day laborers and on protective factors that influence their mental health and COVID 19 mitigation practices.

We intend to use basic demographic, mental health (stressors, depression, isolation and substance use) data collected during the current injury trial to inform the model of the determinants of COVID mitigation practices.

Hypotheses. The proposed project will identify individual risk and protective factors (stressors related to immigration status; familiarity with COVID-19 and its transmission modes and familiarity with the types of actions that are recommended to minimize exposure to COVID-19). We hypothesize that the added stress of the pandemic, coupled with their pre-existing vulnerabilities (e.g. high levels of stress related to their immigration status) will have a negative impact on LDLs' mental health. This will render them less capable of adhering to CDC's COVID-19 prevention guidelines thus putting them at a higher risk of contracting the virus. We also propose that the protective factors identified above may help mitigate the influence of stressors on mental health during the current pandemic. Using a Structural Equation Modeling approach to explore these relationships will allow us to answer fairly complex questions about the associations of multiple constructs at one time. The results will provide a better understanding of the social and personal assets that can be instrumental and serve as intervention targets for this population in the current pandemic.

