The corner observation and data collection will consist of two parts: (1) observe and record information about corner characteristics and worker activities, and (2) a brief group conversation about current events relevant to day laborers to be held with workers present. This second activity does not require specific recruitment procedures as it is intended to get a general impression of events that may influence recruitment, selection and retention of workers during the trial and it may also inform interview procedures. Thus, this activity may involve one or multiple informants whose comments will be recorded anonymously.

III. Latino Day Laborers Virtual COVID-19 Focus Group

Rationale.

The purpose of this research activity will be to engage a group of Latino Day Laborers (LDL) in biweekly discussions about the impact of COVID-19 on (1) their daily life, (2) social relationships, (3) work practices and (4) personal wellbeing. Latino Day Laborers are a vulnerable population with limited access to health care and personal protective equipment. Given the current crisis, this activity is important to chronicle the impact of the pandemic on their lives, as we expect that it will impact them personally and collectively.

In addition, we need to document the way this unprecedented crisis has altered the dynamics at the corners and disrupted the lives of the Latino Day Laborers in order to anticipate the impact of the pandemic on the eventual implementation of our currently planned community randomized trial.

Participants and procedures.

LDLs will be asked to join six group meetings lasting two hours to be held over Zoom every two weeks. The group will consist of 6-8 LDL who are members of the Vales+Tu Community Advisory Board (CAB) and/or volunteers of the Fe y Justicia Workers Center, our community partner.

Prior to the start of the conversations, research staff members will set a time to teach each participant how to use Zoom and to help them get connected. At this time, participant consent will also be obtained. Potential participants will be told the purpose of the virtual focus groups, that they can refuse to answer any questions and that they can stop participating in the discussions at any time. If the potential study participant does not provide informed consent, he will be thanked for his time but will not be able to take part in the focus group.

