Participants will be contacted one month later by phone and will be administered the follow-up survey. Participants will receive a \$30 gift card for completion of the baseline survey. Participants will receive a \$50 gift card for completion of the baseline survey and the individual/group activity. Participants will receive an additional \$30 gift card for completion of the follow-up survey.

We will assess the feasibility of implementing safety measures to mitigate the risk of disease transmission. These will include the use of masks/face shields, gloves, and hand sanitizer by study personnel. We will also provide these materials to LDL. Social distancing will be observed. We will use tape and traffic cones to delineate "rooms" in which surveys and interventions will be delivered. Distancing and the use of masks and hand sanitizer will also be observed by study personnel while in their offices. We will follow departmental guidelines in the case any study personnel exhibits symptoms of infection.

Clinical Trial Description

Study Design

We will conduct a cluster randomized trial of the intervention to determine its efficacy as implemented among Houston LDL. We will use an experimental and control group design with three conditions randomly assigned at the street-corner level, and the intervention delivered at the individual (LDL) level. The treatment arm will include two conditions: (1) individual (Brief Motivational Intervention) and (2) group (Group Problem Solving) interventions. The standard of care control group will consist of (3) a distribution of OSHA 10 safety cards. This will be a five-year study. An individual's

participation would be approximately six months and would comprise a baseline and two-follow-up surveys.

Clinical Trial

Selection of the study population. The study population will be LDL present at study corners.

Inclusion/exclusion criteria. To be eligible to participate in the study, a day laborer must be 18 years of age or older, self-identify as Hispanic or Latino, be present at the corner for the purpose of looking for work, and have been previously hired to work at a corner.

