OSHA 10 Safety Cards. Participants in this standard of care control group will receive four wallet size cards with information about risk reduction strategies to deal with the four hazards responsible for most workplace fatalities in Texas: falls, struck by, heat exposure and cuts. The laminated cards are adapted from OSHA's website publicly available materials in Spanish for workers with limited literacy.

Brief Motivational Intervention (BMI). This intervention is a person-centered, brief yet directive method for enhancing intrinsic motivation change by exploring and resolving ambivalence. Effective use of BMI necessitates the definition of a target behavior, in this case, formulating a plan to reduce injury-related risk behaviors. Sessions will be initiated by exploring working conditions and psychosocial factors (perceptions of injury risk, social norms and self-efficacy) that may influence risk for work related injuries. If the LDL is motivated to change the target behavior, a 'change plan' will be developed. Change plans involve identifying reasons for change, goals in making change, specific actions and timelines, and others who may help the person change. BMI has been shown through clinic-based randomized control trials to increase behavior changes. The goal of the BMI session is to get workers to focus on aspects of their shifting work experience that they feel is within their control in increasing their workplace safety. BMI sessions to be implemented during the VALES+Tú trial are expected to last 30-45 minutes and they will be conducted in one-on-one sessions by a Spanishspeaking facilitator trained to use an injury risk reduction dialogue consistent with standard BMI procedures. The final step in the BMI session will be the development of a personal safety plan to reduce work place risks and a discussion of the following topics: (a) how they will know if their plan is successful, (b) potential obstacles, and (c) what the worker can do if the plan does not work. Finally, each worker will be asked to write and sign a personal pledge ("Mi Promesa") to implement his own safety plan. Fidelity of BMI implementation will be based on two criteria: 1) adherence, or whether the LDL promotor carried out specified procedures as indicated in the manual of procedures, and; 2) competence, based on the skills of the promotor in implementing the intervention.

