Corner selection and assignment. Our recent corner needs assessment study mapped 44 corners in the Houston area bounded by the Sam Houston Tollway, covering about 350 square miles. We will base our sampling design on that number and distribution, and, prior to implementation we will survey corner sites to confirm their stability and identify new corners that may have emerged using the methodology of our Phase I pilot study. The Workers Center Outreach Coordinator will be responsible for visiting and mapping the corners. A "corner" is a) a labor hiring public location such as a street corner, bus stop, gas station or home improvement stores within the designated geographic area, b) an independent hiring site (independence as defined by at least 3 blocks of physical distance from the nearest corner), and c) a hub for day laborers observed seeking employment at that location. Locally, corners range in size from quite small (5 to 10 men) to very large (> 75 men), with the majority

supporting 12 to 30 LDL looking for work on a given day. To reach our enrollment goal of a total of 300 LDL, we plan to randomly sample 30 corners from the total number identified and select an average of 10 LDL at each corner to enroll in the study. As corner sizes vary, we may enroll fewer LDL at some corners than at others. The number of corners/clusters sampled will be kept to the sampling design of 10 per group (total of 30) to maximize statistical power.

Sample size. Sample size was estimated using Monte Carlo simulation procedures. For purposes of the simulation, we made the following assumptions: a cluster randomized design, an intervention condition at the cluster (i.e. street corner) level, 20 interventions corners, split equally across the two intervention conditions, 10 control corners, an intraclass correlation coefficient (ICC) of 0.02, an across-time correlation of outcome measures of 0.5 (derived from our pilot data), a nominal alpha of 0.05, desired power of at least 80%, three measurement waves (one pre-test and two post-test), and attrition between baseline and wave 3 of 30%. A group by time interaction serves as the primary indicator of treatment effect, with a minimum desired detectable interaction parameter estimate of 1.5 units (a value also derived from our pilot data) on the workplace hazards scale. Based on these parameters, we require an average of 10 participants from each of the 30 corners, for a total of 300 participants at baseline.

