[figure not shown]
Analyses. AIM1: Determine the efficacy of VALES+Tú in reducing hazardous exposures at work. Our primary method of longitudinal data analysis will be growth curve modeling using multilevel models (MLM). MLM is a flexible technique that can accommodate individually-varying times of observation, and time-variant and invariant variables as needed. To develop the MLM, we specify a three-level model, with repeated measures nested within individuals nested within corners, thus accounting for the clustered nature of our study design. Using matrix notation, this model takes the form y = XB + Zu+ e for continuous outcomes, where y is n x 1 vector of responses, X is the n x p design matrix of fixed effects **B**, **Z** is the n x q design matrix of random effects \mathbf{u} , and \mathbf{e} is the n x 1 vector of residual errors. Of primary interest is the two-way interaction between intervention status (intervention or control) and time located in the X vector, with random intercepts at the individual and corner levels, both located in the Z vector. The X vector will also contain important covariates as needed. The two-way interaction will indicate whether the intervention has an effect on workplace hazards during the study period, as compared to controls. Consistent with Aim 1, the two treatment groups (Brief Motivational Intervention and Group Problem Solving) will be compared separately against a common control group. Models will be estimated using maximum likelihood estimation.

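### Corners are randomised and fielded with no calendar blocking, and the Aim 1 model has no term for calendar drift in change, so type I error may rise modestly above 5%

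*Combined protocol and SAP*

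**What the plan says.** Under Study Design, the combined protocol and SAP has "three conditions randomly assigned at the street-corner level". Under Statistics, Corner selection and assignment, "we plan to randomly sample 30 corners from the total number identified and select an average of 10 LDL at each corner". The Sample size paragraph assumes "20 interventions corners, split equally across the two intervention conditions, 10 control corners" and "an intraclass correlation coefficient (ICC) of 0.02". None of these sections gives a randomisation method, stratification, blocking, fielding order or enrolment period. The only calendar anchor for the trial is a planned start in spring 2021 (Small Pilot Feasibility Study). A study schedule is listed as an attachment but is not in the text supplied.

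For Aim 1, "Of primary interest is the two-way interaction between intervention status (intervention or control) and time". The random effects are intercepts for individual and corner. Covariates are left open, to be added as needed. The model is said to accommodate varying observation times and time-varying variables, but no calendar term is named.

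Two statements suggest that conditions may change over the calendar. The control cards address "the four hazards responsible for most workplace fatalities in Texas: falls, struck by, heat exposure and cuts". The rationale for the virtual focus group says that "this unprecedented crisis has altered the dynamics at the corners".

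The follow-up interval is not consistent. It is one month in the header and in Study Procedures, about six months with two follow-ups in Study Design, and one to two months in the COVID-19 Supplemental Study.

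**The concern.** Field teams must visit thirty corners, and that probably takes months. The primary effect is a difference between arms in change from baseline. A seasonal difference in level is removed by the baseline measure. A difference in drift between the two surveys is not: a corner started as the weather warms may change differently from one started as it cools, whatever its arm.

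Drift of this kind is shared by all men at a corner, so it is corner-level variation in change. A model with random intercepts only carries corner differences in level but has no corner-by-time component. It therefore tests the arm-by-time contrast against a standard error that is too small. With 10 corners per arm, chance imbalance in start dates is not negligible. What is at stake is the type I error and precision of both primary contrasts. If fielding order were tied to arm, bias would be at stake as well.

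**Working it through.** **The plan's own figure.** N = 300 comes from a simulation whose SD, time coding and attrition pattern are not given, so it cannot be strictly reproduced. With the pilot-derived SD below, 100 per arm, ICC 0.02 and 30% loss, power for 1.5 units is 61% on a change score, 74% with baseline adjustment, and over 99% if 1.5 units is a slope per wave. The figure is neither confirmed nor refuted, and this point does not depend on it.

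**Inputs**
- SD of change, from the pilot test (means 17.7 and 15.7, N = 63, t = 4.26): 2.0 × √63 / 4.26 = 3.73. Rounding of the means allows 3.54 to 3.91.
- Followed per arm: 100 × 0.70 = 70, or 7 per corner. This applies the plan's wave-3 attrition.
- Seasonal cycle: sinusoid with a 12-month period and amplitude A = 1, 2 or 3 units (peak to trough 2, 4 or 6). **This is an assumption.** The documents give no seasonal size and do not list the scale items.
- Fielding spread evenly over 12 months (assumed), follow-up at one month, no true effect.

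**SE without drift:** 3.73 × √(2/70) = 0.630.

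**Size of drift.** Over one month the drift has amplitude 2A·sin(π/12) = 0.518A, so its SD across a year of start dates is 0.518A/√2 = 0.366A.

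**Random order, by formula**
- True SE = √(0.630² + 2(0.366A)²/10)
- SE seen by an intercept-only model = √(2(3.73² + (0.366A)²)/70)

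| A | True SE | Model SE | Ratio | Type I error | Information lost, 1 − (0.630/true SE)² |
|---|---|---|---|---|---|
| 1 | 0.651 | 0.633 | 1.03 | 5.7% | 6% |
| 2 | 0.710 | 0.642 | 1.11 | 7.6% | 21% |
| 3 | 0.799 | 0.657 | 1.22 | 10.6% | 38% |

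**Simulation, same setting (6,000 runs)**

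| Fielding order | Mean bias, A = 1, 2, 3 | Type I error, A = 1, 2, 3 |
|---|---|---|
| Random | about 0 | 6.0%, 8.2%, 11.1% |
| Blocks of three, one per arm | about 0 | 4.7%, 4.3%, 4.3% |
| Arm by arm | 0.52, 1.06, 1.60 units | 13%, 38%, 71% |

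With fielding over 6 months, random order gives 5.4%, 7.6% and 10.7%.

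**Six-month follow-up.** The drift amplitude is then 2A·sin(π/2) = 2A. Random order gives type I error of 7% to 35% across the amplitudes and the two fielding periods.

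**How uneven random order is.** Over 12 months of fielding, the median gap between two arms' mean start dates is 1.1 months. It exceeds 3 months in about 5% of randomisations.

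**Analysis-only remedies, one-month follow-up, random order.** Season in three or four categories leaves type I error at about 6% to 10%, because most baseline and follow-up pairs fall in the same category. One sine and one cosine term in survey date bring it back to about 5%. That result is favourable, since the simulated drift was itself a sinusoid.

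**The case against.** Assignment is random. With no rule tying fielding order to arm, the natural reading is that the two are independent, so expected bias is zero. That stands. A reader might infer from the silence on scheduling that the arms are fielded in different seasons and the primary comparison is biased. The documents do not support this: no passage plans to work arms in runs, and the schedule attachment was not available to check. The bias in the arm-by-arm row is conditional on that scenario.

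Seasonality of the outcome is also an inference. The list of hazards describes the control cards, not the items of the scale, and the remark on the pandemic justifies a pre-trial focus group. Neither says that one-month change varies by calendar month. That stands too.

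A reader might also assume a large corner-level drift, say an SD of 0.75 to 1.0 units, which costs 22% to 33% of the information. At one-month follow-up this needs amplitudes of 0.75/0.366 = 2.0 to 1.0/0.366 = 2.7 units, a peak-to-trough swing of about 4 to 5.5 units on a scale with an SD near 3.73. Fielded over a year, such swings alone would imply a between-corner ICC, (A²/2)/(A²/2 + 3.73²), of about 0.13 to 0.21, against the plan's 0.02. For A = 1 the same formula gives 0.5/(0.5 + 13.9) = 0.03. The lower end of the range therefore fits the plan's own assumptions better.

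Finally, the wording on covariates would allow a calendar term. It does, but it does not commit to one, and a term chosen after the data are seen is weaker than one fixed beforehand.

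**Conclusion.** The gap is real and its consequence is modest. Nothing in the documents balances arms over calendar time, and the stated Aim 1 model has no component for corner-level variation in change. If fielding order is independent of arm there is no systematic bias. Nominal 5% type I error becomes about 6% to 11% at assumed amplitudes of 1 to 3 units and one-month follow-up, with the lower end more plausible. It is larger if the six-month interval in Study Design applies, so that inconsistency should be settled as well.

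The stronger conclusion, that season biases the treatment effect by a large share of the 1.5-unit target, holds only if arms are fielded in runs. The documents neither plan nor exclude that.

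The result rests on an assumed sinusoid, a back-calculated SD, 7 men followed per corner, and fielding over 6 or 12 months. It supports a cheap improvement and does not show that the design is invalid.

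**What to change.** 1. State the fielding order and the enrolment period.
2. For corners not yet fielded, randomise and release them in calendar blocks of three (one Brief Motivational Intervention, one Group Problem Solving, one control), started within the same few weeks. Include block and block-by-time in the Aim 1 model. This also protects against pandemic shifts of any shape.
3. For corners already fielded, pre-specify a smooth time-varying term in the calendar date of each survey, for example one sine and one cosine term. Do not use three or four season categories, which miss drift within a season. The version is dated October 2021 and the COVID-19 supplement describes the parent study as already implemented, so this route may apply to many corners. A random corner-by-time effect would further guard the error rate against drift that is not sinusoidal.

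Costs: N stays at 300. Teams must be ready to deliver all three conditions in the same weeks. Two smooth terms use two degrees of freedom. Ten full blocks would use 9 for block-by-time, taking corner-level degrees of freedom for change from 30 − 3 = 27 to 18. Follow-up survey dates must be kept: the Survey Completion Tracking form documents only the date of consent.
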